$$\text{logit}(\Pr\{T_i = 1\}) = \text{logit}(\pi_i^T) = \alpha_0 + \alpha_1 Y_{i0} + \alpha_2 \text{Age} + \alpha_3 \text{PTA}$$

The fitted values from this model for participant i is $\hat{\pi}_i^T = \text{expit}\{\mathbf{X}_i' \hat{\boldsymbol{\alpha}}\}$, where $\text{expit}(\cdot)$ is the inverse of the logistic function. The propensity score for participant i is $\hat{\pi}_i^{PS} = T_i \hat{\pi}_i^T + (1 - T_i)(1 - \hat{\pi}_i^T)$.

After the propensity score is created, a logistic regression model will be used to model the probability of being observed at follow-up according to baseline characteristics (the outcome measured at baseline, age, PTA, and treatment assignment). The propensity score model will be defined as follows:

$$\text{logit}(\Pr\{R_i = 1\}) = \text{logit}(\pi_i^R) = \gamma_0 + \gamma_1 Y_{i0} + \gamma_2 \text{Age} + \gamma_3 \text{PTA} + \gamma_T T_i$$

The fitted values from this model for participant i is $\hat{\pi}_i^R = \text{expit}\{\mathbf{X}_i' \hat{\boldsymbol{\gamma}} + \gamma_T T_i\}$. An inverse probability weight for each participant is then created: $w_i = 1/(\hat{\pi}_i^R \hat{\pi}_i^{PS})$. Inverse probability weights above 20 will be set to 20 to mitigate the influence of individuals with large inverse probability weights.

After the inverse weight is created, this weight is used in a g-computation step. The model used in g-computation involves transforming the outcome to the range $[0, 1]$, and performing a weighted logistic regression (Gruber & van der Laan, 2010). If an outcome has no maximum value, no transformation is performed. The outcome for individual i , Y_{i1} , is mapped to the range $[0, 1]$: if y_{MAX} and y_{MIN} respectively denote the maximum and minimum possible values of the outcome, this transformation and its inverse are given by:

$$g(y) = (y - y_{MIN}) / (y_{MAX} - y_{MIN})$$

$$g^{-1}(y) = y(y_{MAX} - y_{MIN}) + y_{MIN}$$

For example, the primary outcome is the change in HHIE from baseline, this ranges from $y_{MIN} = -40$ to $y_{MAX} = 40$. The transformed outcome on the $[0, 1]$ interval is then modeled using a logistic regression model, weighted by the inverse probability weights described above:

$$\text{logit}(g(Y_{i1})) = \beta_0 + \beta_1 Y_{i0} + \beta_2 \text{Age}_i + \beta_3 \text{PTA}_i + \beta_T T_i$$

This model can be fit using an overdispersed binomial or ‘quasibinomial’ family of generalized linear model. In R, this involves using the `glm` command with `family = “quasibinomial”` argument, and in Stata, this can be fit using the `fracreg` command with a logit link. For secondary outcomes that do not have a defined range, a weighted linear regression model is fit, weighted by the inverse probability weights described above:

$$Y_{i1} = \beta_0 + \beta_1 Y_{i0} + \beta_2 \text{Age}_i + \beta_3 \text{PTA}_i + \beta_T T_i + \varepsilon_i$$

Using the appropriate weighted regression model, a predicted outcome is generated for each participant under assignment to treatment and control. For the logistic regression model:

$$\hat{\eta}_i^{(1)} = \text{expit}(\hat{\beta}_0 + \hat{\beta}_1 Y_{i0} + \hat{\beta}_2 \text{Age}_i + \hat{\beta}_3 \text{PTA}_i + (\hat{\beta}_T \cdot 1))$$

$$\hat{\eta}_i^{(0)} = \text{expit}(\hat{\beta}_0 + \hat{\beta}_1 Y_{i0} + \hat{\beta}_2 \text{Age}_i + \hat{\beta}_3 \text{PTA}_i + (\hat{\beta}_T \cdot 0))$$

For the linear regression model:

$$\hat{\eta}_i^{(1)} = \hat{\beta}_0 + \hat{\beta}_1 Y_{i0} + \hat{\beta}_2 \text{Age}_i + \hat{\beta}_3 \text{PTA}_i + (\hat{\beta}_T \cdot 1)$$

$$\hat{\eta}_i^{(0)} = \hat{\beta}_0 + \hat{\beta}_1 Y_{i0} + \hat{\beta}_2 \text{Age}_i + \hat{\beta}_3 \text{PTA}_i + (\hat{\beta}_T \cdot 0)$$

The doubly robust estimator for the average treatment effect is calculated as the average difference between counterfactual outcomes. If the outcome was originally transformed, this average is taken after they are transformed back to the original scale of the outcome:

$$\hat{\delta}_{DR} = \frac{1}{n} \sum_{i=1}^n \left(g^{-1}(\hat{\eta}_i^{(1)}) - g^{-1}(\hat{\eta}_i^{(0)}) \right)$$

For untransformed outcomes, no inverse transformation is required:

$$\hat{\delta}_{DR} = \frac{1}{n} \sum_{i=1}^n \left(\hat{\eta}_i^{(1)} - \hat{\eta}_i^{(0)} \right)$$

The advantage of the transformation is that the fitted values $g^{-1}(\hat{\eta}_i^{(t)})$ are constrained to the range of their respective outcomes. While Gruber and van der Laan (2010) use the Targeted Maximum Likelihood Estimator rather than the DR-WLS estimator proposed here, the same principles apply.

Confidence intervals will be obtained using bias corrected and accelerated (BCa) bootstrap resampling procedure with 10,000 replicates. Imputation of any missing baseline covariates will be performed within each bootstrap sample.

The primary analysis will utilize the HHIE-S score obtained in-person whenever possible irrespective of study window and will use HHIE-S Scores obtained over the phone when an in-person visit was not obtained. Sensitivity analyses will include repeating the analysis with exclusion of outcomes obtained beyond 30 days outside of the study window: this will involve a new missing data indicator $R_i^S = 1$ if Y_{i1} is observed within the study window, and $R_i^S = 0$ otherwise.

Secondary Analyses: The secondary analyses will follow similarly from the primary analysis, using the same doubly robust estimator as described above. Secondary outcomes are listed in table 4: secondary outcome models will have the same specification for the outcome model (treatment indicator and linear terms for the baseline value of the outcome, age, and PTA) and the propensity score model (treatment indicator and linear terms for the baseline value of the outcome, age, and PTA).

Planned secondary analyses will be performed on the primary outcome, communication function as measured by HHIE-S, using the complier average causal effect (CACE) of the intervention, following a methodology similar to Stuart and Jo (2015). In this analysis, individuals are conceptualized as belonging to four latent classes, known as principal strata, which are unaffected by randomization. These strata include ‘compliers,’ who comply with whichever intervention assigned to them, ‘always takers,’ who will always take the treatment regardless of their treatment assignment, ‘never takers,’ who will never take

the treatment regardless of their treatment assignment, and ‘defiers,’ who will take whichever treatment they are not assigned. Adherence with the intervention will be defined as attending both scheduled intervention meetings and using the amplification device 1 or more hours per day at 3-months post-intervention. Since the HEARS intervention is not available outside of the study, we assume that there are no ‘always takers,’ and similarly, we assume that there are no ‘defiers.’

This analysis will be similar to the analysis described above, with an additional step added in creating the weights for the weighted regression. We will fit a logistic regression model for the probability of adherence or compliance, denoted A_i , among those in the immediate treatment group (wave 1):

$$\text{logit}(\Pr\{A_i = 1|T_i = 1\}) = \text{logit}(\pi_i^A) = \theta_0 + \theta_1 Y_{i0} + \theta_2 \text{Age} + \theta_3 \text{PTA}$$

This model will be used to predict the probability of adherence in the wait list control group (wave 2) based on these characteristics. A propensity score will be calculated as follows:

$$1/\hat{\pi}_i^A = \begin{cases} 1: T_i = 1, A_i = 1 \\ 0: T_i = 1, A_i = 0 \\ 1/\text{expit}\{X_i'\hat{\theta}\}: T_i = 0 \end{cases}$$

Since compliance status (A_i) can only be observed among those in the treatment arm, those in the control arm ($T_i = 0$) will have their propensity to comply predicted using the regression model fit among individuals in the treatment arm ($T_i = 1$). An additional weight will be created as follows:

$$w_i^C = 1/(\hat{\pi}_i^R \hat{\pi}_i^{PS} \hat{\pi}_i^A)$$

This weight w_i^C , which incorporates the compliance propensity score $\hat{\pi}_i^A$, will be used in the estimation procedure described above instead of w_i . The goal of this procedure is to re-weight the data to not only account for differences between arms at baseline and differences due to attrition, but also to account for differences between observed compliers in Wave 1 and waitlisted controls in Wave 2.

This method uses the assumption of principal ignorability (PI), which assumes that principal stratum membership (‘compliers’ vs. ‘never takers’) is conditionally independent of the potential outcomes given the observed covariates. Additional exploratory analyses may be conducted under different causal inference assumptions or utilizing different predictors of treatment adherence.

Exploratory subgroup analyses will be performed to examine the potential influence of factors on participant outcomes, including 1) cognition (normal cognition MoCA total score ≥ 26 vs. Cognitive impairment MoCA total score < 26 ; including adjustment of 1 additional point for individuals with 12 years or fewer of education), 2) severity of hearing loss (mild hearing loss ≤ 40 dB better ear speech PTA vs. More severe hearing loss > 40 dB better ear speech PTA) and 3) education (High school or less vs. Greater than high school). When subgroups contain fewer than 30 individuals with observed outcome data or rates of missingness that pose convergence problems for inverse probability weight models, alternative methods may be considered.

Missing Data: As stated above, instruments with any missing items (e.g. “Refused”, “Don’t Know”) will be coded as missing unless there are published criteria for handling missing items. Frequency and patterns of missing data will be tabulated in aggregate and by treatment arm. The doubly robust estimator is valid under the assumption that data are missing at random: that the degree of missingness does not depend on unobserved variables or the values of the missing data. Additionally, a

supplementary table will compare baseline characteristics between those with missing 3-month post-randomization outcomes to those with complete data both in aggregate and by treatment arm.

If an individual's baseline outcome is missing, and the outcome of interest is a baseline change score, imputed values will only be used to calculate propensity scores and inverse probability weights: since the original value was not observed, the change from baseline will be considered missing.

Risks and Potential Harm: The risks involved in participation in the study are believed to be low. There is a theoretical risk of noise exposure related to use of an amplification device, primarily if the device malfunctions. The risk of noise exposure is minimized with volume limitations as part of the device design. All products used in the study are commercially available and all models used in the study are considered over-the-counter devices.

Other than the intervention failing to produce an effect, there are no known possible adverse effects documented in the literature or experienced in prior pilot studies involving over-the-counter amplification devices and the HEARS intervention. All devices and intervention materials have been either previously used in pilot studies or are currently used by consumers in the United States with no known harmful effects.

During the study, survey questions regarding depression, social isolation, and loneliness will be posed to participants. All participants receive a brochure detailing information regarding both audiological and otological care as well as behavioral health resources. During survey administration, depression severity is assessed using PHQ-9 (score 0-27). Participants who score of 15 or above will be counseled to speak with their primary care physician. An offer to help contact their primary care physician is given and effort made to relay survey score results to their primary care office is made if permission is given. The occurrence is noted and resources provided to the participant. In addition, if the participant mentions any level of intention to harm self or others, verbal contract not to harm self is collected and adverse event protocol is followed if immediate threat to self or others is apparent. In the case of participants who score 5-14 on the PHQ-9, the occurrence is also noted and resources provided to the participant. Occurrences where the PHQ-9 score is 5 or above are noted, but the occurrence is not considered an adverse event.

Given the low risk related to the HEARS intervention, no to few adverse events are expected. All adverse events are recorded by the research coordinator and immediately reported to the Principal Investigator. The research coordinator will collect information regarding the adverse event from the participant and/or informant, including details surrounding the event to inform assessment of the severity of the event, causality, and the relatedness to the intervention and trial involvement.

Information on adverse events will be summarized in terms of severity, causality, and relatedness to the study intervention and information presented in the final trial results.

Statistical Software: Data management and analyses will be conducted using the R environment for Statistical Computing and Stata as needed. In R, 95% BCa bootstrap confidence intervals will be calculated using the boot package.

References:

Gruber, S., & van der Laan, M. J. (2010). A Targeted Maximum Likelihood Estimator of a Causal Effect on a Bounded Continuous Outcome. *The International Journal of Biostatistics*, 6(1):1-14.

<https://doi.org/10.2202/1557-4679.1260>

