- c. Further description was added to the primary analysis, including the commands in Stata and R for the outcome regression model.
- d. The formula for calculating the weights in the Complier Average Causal Effect model was corrected, and additional explanation of the method was added.

Section 2: Introduction

Background and Rationale: Hearing aids, along with adequate counseling and education, form the foundation of a comprehensive approach to hearing health care. Hearing aids can improve audibility, communication, and may help promote better general health and social engagement in older adults (Boi et al., 2012). While an important component of hearing health care, hearing aids are underutilized. Only 15% of older adults undergo hearing screening and less than 20% of older adults with demonstrated hearing loss use hearing aids (Kochkin, 2009; Popelka et al., 1998; Gates et al., 1990). This demonstrates a gap in care that the NIDCD, Healthy People 2020, and the National Academies of Science, Engineering, and Medicine (NASEM) have identified and, subsequently, called for the development of additional models of affordable and accessible hearing health care (Donahue et al., 2010; NASEM, 2016).

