Wave 2: 3-Months Post-Randomization (Repeat Baseline*)	N/A	Goal: 3-months post-randomization Window: Up to 6 months post randomization
3-Months Post-Intervention	Goal: 3-months post-intervention Window: Up to 6 months post intervention	Goal: 3-months post-intervention Window: Up to 6 months post intervention
12 Months Post-Intervention	Goal: 12 months post-intervention Window: Up to 18 months post-intervention	Goal: 12 months post-intervention Window: Up to 18 months post-intervention

Table 2: Windows allowed for each follow-up visit. The efficacy of the HEARS intervention will be assessed at the 3-month post-randomization visit*. After this visit, the delayed treatment group will be offered the intervention, and they will have a 3 months post-intervention study visit. Both immediate and delayed treatment groups will have a 12-month post-intervention follow-up visit.

The primary endpoint is the 3-month post-randomization visit. After this assessment, individuals in the delayed treatment group ('Wave 2') will be offered the intervention and followed up 3 months after the intervention has been administered (with a window up to 6 months post-intervention delivery). Both immediate ('Wave 1') and delayed ('Wave 2') treatment groups will have a 12-month post-intervention follow-up visit. Only the baseline visit and 3-month post-randomization visits will be used to assess the efficacy of the intervention.

[figure not shown]

Figure 1: A diagram of study visits by treatment arm. Dotted boxes indicate visits with community health workers (CHWs) and solid boxes indicate visits with study staff.

Section 4: Statistical Principles

Hypothesis tests and Confidence Intervals: This study was designed to achieve at least 90% power to detect an effect size of $\delta \geq 0.6$ on the Hearing Handicap Inventory for the Elderly Short Form (HHIE-S) while maintaining a familywise type I error rate of $\alpha = 0.05$. Since there is only one contrast of interest in one outcome at one endpoint, the average treatment effect at 3-months post randomization between immediate (Wave 1) and delayed (Wave 2) treatment groups, no adjustment for multiplicity is needed. A 95% confidence interval will be reported for the primary outcome, and for all hypothesis-generating secondary outcomes. All hypothesis tests will be two-sided, using a 5% significance level.

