Screening data: Variables that will be tabulated to describe the representativeness of the sample are summarized in table 3.

Eligibility Criteria: Participant inclusion and exclusion criteria are as follows:

- Inclusion criteria:
 - Age 60 years or older
 - English-speaking
 - Aural-oral verbal communication as primary communication modality
 - Post-lingual hearing loss (Audiometric pure tone averages [0.5-4kHz] in both ears >25 dB)
 - Does not currently use a hearing amplification device or hearing aid
 - Signed informed consent to participate in all study related activities
 - Willing to regularly use listening device once provided for the remainder of their time in the study
 - Hearing handicap as measured by HHIE-S score ≥ 8
 - Able to follow study instructions
- Exclusion criteria:
 - Evidence of ear disease or pathology requiring further medical evaluation

CONSORT Criteria:

- Assessed for eligibility: Those who were screened for eligibility in the study
- Excluded: Those who did not meet study eligibility criteria
 - Age: Number of people who did not meet age eligibility
 - English Fluency: Number of people who did not meet English fluency eligibility
 - Study commitment: Number of people who did not meet study commitment eligibility
 - Hearing Aid History: Number of people who did not meet hearing aid history eligibility
 - Otologic Screen Score: Number of people who did not meet otologic screen eligibility
 - PTA <25dB: number of people who did not meet minimum PTA threshold eligibility in their better ear
 - Screening Reliability: number of people who did not meet screening reliability eligibility

- HHIE<8: number of people who did not meet minimum HHIE score eligibility
- Consented: Number of eligible individuals who consented to be randomized
- Randomized: Number of people who were randomized
- Allocation to Immediate Intervention: Number of people allocated to receive the intervention immediately
 - Received Intervention: number of people who successfully completed the intervention within delivery window (1 month from baseline visit)
 - Delayed intervention: number of people who successfully completed the intervention, but outside of delivery window (over 1 month from baseline visit)
 - Did not receive Intervention: Number of people who did not successfully complete the intervention due to refusal, withdrawal, or loss to follow up

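### Secondary CACE analysis: the compliance weight for waitlist controls is printed as the reciprocal of the predicted probability of complying, where the probability itself is needed

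*SAP*

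**What the plan says.** SAP Section 6, Secondary Analyses, plans a CACE analysis of the primary outcome. Adherence means attending both sessions and using the device at least one hour a day at 3 months post-intervention. A logistic model for adherence on baseline HHIE-S, age and PTA is fitted in Wave 1 and used to predict adherence in Wave 2.

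The SAP then displays the reciprocal of the compliance score: 1 for Wave 1 compliers, 0 for Wave 1 non-compliers, and, for waitlist controls, "1/\text{expit}\{X_i'\hat{\theta}\}: T_i = 0". This is multiplied into the combined weight, "w_i^C = 1/(\hat{\pi}_i^R \hat{\pi}_i^{PS} \hat{\pi}_i^A"), which replaces the ordinary weight in the regression and g-computation steps.

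The stated aim is to "account for differences between observed compliers in Wave 1 and waitlisted controls in Wave 2". The identifying assumption is also stated: "This method uses the assumption of principal ignorability (PI").

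The outcome model is the one used elsewhere, with "treatment indicator and linear terms for the baseline value of the outcome, age, and PTA", so it has no treatment-by-baseline term. The log of changes from version 1.0 to 1.1 in SAP Section 1 records that "The formula for calculating the weights in the Complier Average Causal Effect model was corrected", so the printed formula is the revised, current text. The same log says that all changes after version 1.0 followed unblinding of outcomes.

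**The concern.** Dropping Wave 1 non-compliers leaves a selected treated group: people whose covariates make adherence likely are over-represented. The compliance weight exists to select the controls in the same way. Dividing by the predicted probability does the reverse. A control with predicted adherence 0.4 receives a factor of 2.5, and one with 0.8 receives 1.25, so the control least like a complier counts double.

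This weight is the one step the SAP adds to turn its intention-to-treat estimator into a CACE. If it points the wrong way, the comparison of compliers with controls rests on the main-effects regression alone. Anyone reproducing the CACE from the public SAP would also implement the wrong weight.

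**Working it through.** **Inputs.** From SAP Section 6: the three-line compliance factor, the combined weight, the adherence covariates and principal ignorability. From SAP Section 3: 1:1 allocation. The documents give no adherence rate and no predictors of adherence, so every rate and slope below is an assumption.

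**Step 1, algebra.** Let f(X) be the covariate density, the same in both arms by randomisation, and e(X) the probability of complying given X.

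- Observed Wave 1 compliers (factor 1) have density proportional to f(X)e(X).
- Controls weighted by h(X) have density proportional to f(X)h(X).
- The two match only if h is proportional to e. Under principal ignorability, E[Y(0) | complier] = E[e(X)Y | T=0] / E[e(X) | T=0].
- The printed h = 1/e gives f(X)/e(X). The two weights agree only when e(X) is constant.

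**Step 2, exact two-stratum check.** Equal strata, adherence 0.8 and 0.4. Share in the high-adherence stratum:

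- Compliers: 0.5×0.8 / (0.5×0.8 + 0.5×0.4) = 0.40/0.60 = 66.7%
- Unweighted controls: 50.0%
- Printed weight: (0.5/0.8) / (0.5/0.8 + 0.5/0.4) = 0.625/1.875 = 33.3%
- Weight e(X): 0.40/0.60 = 66.7%

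The gap is 16.7 percentage points with no compliance weight, 33.3 as printed and 0 with e(X). With adherence 0.6 in both strata, all shares are 50%.

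**Step 3, covariate gap.** Absolute difference in standardised baseline HHIE-S between compliers and controls, by simulation:

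| Adherence | Log-odds slope per SD | No compliance weight | Printed | e(X) |
|---|---|---|---|---|
| 60% | 0.5 | 0.19 | 0.38 | 0 |
| 60% | 1.0 | 0.34 | 0.74 | 0 |
| 80% | 0.5 | 0.09 | 0.19 | 0 |
| 80% | 1.0 | 0.17 | 0.36 | 0 |

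With slopes -0.5 and -1.0 the printed gap is 0.41 and 0.85 at 60%, and 0.21 and 0.42 at 80%. The 80% rows are included because eligibility requires "Willing to regularly use listening device once provided for the remainder of their time in the study", which may make adherence high.

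**Step 4, bias in the CACE estimate.** The SAP steps were simulated with these assumptions: baseline HHIE-S truncated normal on 8 to 40 (mean 21.7, SD 6.9), residual SD 7, full follow-up, and the cap of 20 carried over to the CACE weight. Bias comes from very large samples, and the sampling SD from 1,500 trials of n = 150 × 0.8 = 120. With a constant effect and linear outcome, bias is 0.02 points or less. With an effect of -5.0 - 2.0z (z = standardised baseline) and a linear outcome, bias in HHIE-S points is:

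| Adherence | Slope | Printed | No compliance weight | e(X) |
|---|---|---|---|---|
| 60% | 0.5 | +0.19 | +0.14 | -0.01 |
| 60% | 1.0 | +0.32 | +0.23 | -0.01 |
| 60% | -0.5 | -0.18 | -0.13 | +0.01 |
| 60% | -1.0 | -0.26 | -0.20 | +0.03 |
| 80% | 0.5 | +0.15 | +0.09 | 0.00 |
| 80% | 1.0 | +0.26 | +0.14 | 0.00 |
| 80% | -0.5 | -0.14 | -0.07 | +0.02 |
| 80% | -1.0 | -0.25 | -0.14 | +0.02 |

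The inversion therefore adds 0.05 (0.19 - 0.14) to 0.12 (0.26 - 0.14). The rest arises because the outcome model has no treatment-by-baseline term. Positive bias is towards the null.

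With a curved control outcome and a varying effect, still at 60% and 80%, the printed bias was 0.04 to 0.40 in 15 of 16 scenarios and 0.49 in one. With e(X) it was 0.05 or less.

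**Step 5, what the regression rescues.** In a separate linear approximation with three covariates, a constant effect and a true CACE of -0.600, weighting alone gave -0.854 with the printed weight and -0.597 with e(X). Adding the regression gave -0.596 with either. With a varying effect (truth -0.656), weight plus regression gave -0.630 as printed, -0.637 with no compliance weight and -0.656 with e(X).

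**The case against.** **Importance.** The CACE is one secondary analysis. The SAP rests efficacy on a single intention-to-treat contrast, and SAP Section 4 promises confidence intervals "for all hypothesis-generating secondary outcomes", so these results are not confirmatory. In the linear runs the inversion adds at most 0.12 points to a sampling SD of 1.4 to 1.6. This stands: the reason to correct the formula is that it is wrong in principle and cheap to fix.

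**Balance is not bias.** A wider covariate gap does not always mean more bias than no weight. At 40% adherence with a linear outcome and varying effect, the printed weight was slightly less biased (0.13 to 0.20 against 0.14 to 0.24). The same held in one of the 16 curved scenarios (0.23 against 0.33). This stands too. Yet at 40% adherence curvature took the printed bias as high as 0.74, so the small figures are not guaranteed.

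**Assumed inputs.** The simulation inputs come from no document, and full follow-up means the attrition weight was never exercised. The second decimal should not be over-read. The algebra in Step 1 does not depend on them.

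**Double robustness.** The SAP claims it for missing data, not for compliance. That is fair. The narrower point is that the compliance weight gives no protection if the regression is misspecified.

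**A misprint.** If the left side of the display were meant to be the score itself, Wave 1 non-compliers would have score 0 and infinite weight. The 1 and 0 lines make sense only for the reciprocal, and the combined weight is consistent with that. The code may still be right. The documents do not show it.

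**Conclusion.** The printed control weight is inverted, and no other part of the SAP overrides it. Under the SAP's own assumption, controls need e(X). When adherence depends on the covariates, the printed factor moves controls away from compliers, roughly doubling the gap in the cases tabulated. When adherence does not depend on them, it does no harm.

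The likely effect on the estimate is small: 0.14 to 0.32 HHIE-S points with a linear outcome, varying effect and 60% to 80% adherence, about a fifth of one sampling SD or less. Its direction is unknown. In those runs it was towards the null when adherence and benefit vary with baseline in the same direction, and away from it when they vary in opposite directions. Low adherence combined with a curved outcome could make it larger.

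The attrition and treatment-propensity weights still do their work, and the primary analysis does not use this factor. The point should be fixed but is of modest weight. Confidence is high about the formula; whether any reported result is affected is unknown.

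**What to change.** Define a compliance factor c directly: 1 for Wave 1 compliers, 0 for Wave 1 non-compliers, and expit(X'theta-hat) for waitlist controls. Write the combined weight as c divided by the product of the follow-up probability and the treatment propensity score. The three-line display, the combined-weight line and the sentence calling the compliance term a propensity score must change together. Changing only the control line would imply a compliance probability above 1. State whether the cap of 20 applies to this weight.

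Then check the analysis code. If it follows the printed formula, rerun the CACE, report results under both weights, and state that the correction was made after unblinding. If it already uses e(X), correct the SAP text only. The cost is a few lines of SAP text, one code check, and at most one rerun and one disclosure sentence. No new data are needed.
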